Please note that source data collected as part of routine clinical care may be used to complete CRFs as long as the window between prior data collection and operative procedures does not exceed six months. This includes previously performed POP-Q exams as well as previously collected questionnaires.

Randomization

Randomization will be assigned using RedCAP in the operating room *immediately prior* to mesh graft attachment to the vagina. Both types of sutures will be available at each site. Participants will be randomized to 2-0 GoreTex/CV4 GoreTex (depending on availability of Stitchkit) versus 2-0 PDS in blocks with block sizes of 2, 4 and 6 for each of the 5 sites. Randomization will be stratified by site.

Surgery (\leq 3 months from Baseline Visit)

Study data for the surgical procedures includes the Surgical Procedures Form and review of adverse events.

- Surgical Procedures Form
- Review of Adverse Events (if applicable)

Laparoscopic or Robotic Approach

Prior to sacral colpopexy all participants of the trial will undergo total laparoscopic hysterectomy (with or without robotic assistance) with or without bilateral salpingoophorectomy (at the discretion of the patient and surgeon).

Laparoscopic sacral colpopexy will be performed with or without robotic assistance. The configuration of the incisions is not standardized.

1. Total laparoscopic hysterectomy (with or without robotic assistance) will be performed in standard fashion and the uterus will be delivered through the vagina with no power morcellation performed. The vaginal cuff will be closed using an absorbable suture in 1 layer (suture type at the discretion of the operating surgeon). Closure of the vaginal cuff through a transvaginal approach is not allowed.
2. The same ultra-lightweight Type 1 polypropylene mesh (Upsylon, Boston Scientific) will be used for all study subjects.

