3. Graft placement on the vagina includes placement on the anterior and posterior vaginal walls. The vesicovaginal and rectovaginal spaces will be opened. The anterior graft will have an attachment that is at least 4 cm long on the anterior vagina with at least 4 sutures. The graft can extend toward the urethrovesical junction but not beyond the UVJ. The posterior graft will be at least 4 cm long and attach to the posterior vagina with at least 4 sutures placed on the posterior vaginal wall. The posterior graft can extend toward the perineal body but cannot be anchored into the perineal body. The sacral arm of the mesh must be attached directly to the anterior longitudinal ligament with at least **2 permanent sutures** (suture type at the discretion of operating surgeon).
4. Closure of the peritoneum over the mesh may be done at the discretion of the operating surgeon.
5. Diagnostic cystoscopy is required after completion of case to confirm intact urothelium and patent ureters.

Optional Additional Procedures

Midurethral sling for treatment or prevention of stress incontinence

1. The surgeon can use any type of full-length mid-urethral, monofilament, polypropylene, sling (retropubic or transobturator).
2. The sling should be done through a separate incision from any other proximal anterior vaginal wall incisions, and dissection should not extend distal to the urethrovesical junction.

Posterior colporrhaphy

1. Posterior repair may be performed at the discretion of the surgeon if the patient has posterior wall prolapse following the apical support procedure as indicated by Bp \geq -1 on non-straining exam under anesthesia.
2. The surgeon may use a traditional posterior colporrhaphy or defect directed technique.

Anterior colporrhaphy

1. Anterior colporrhaphy may be performed at the discretion of the surgeon if the patient has anterior wall prolapse following the apical support procedure, Ba \geq -1 on non-straining exam under anesthesia. Otherwise it is at the discretion of the surgeon.

Urethropexy

1. Robotic/laparoscopic urethropexy may be performed at the discretion of the surgeon.

Follow-Up Visits

Participants will be scheduled for follow-up visits as outlined in Table 1 (Data Collection Schedule) below. The follow-up visit schedule begins from the day the subject is discharged (e.g. leaves hospital/clinic) post-procedure and includes visit windows counted in calendar days.

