Participant contact information will be reviewed at each follow-up visit. All efforts will be made by site staff to ensure minimal loss to follow-up of participants and will follow a site-specific loss to follow-up plan. This plan may include efforts such as telephone follow-up, Investigator-patient counseling, visit reminder tools, patient stipends, and/or other communication methods.

Week 6 Visit (-2 weeks/+4 weeks)

The primary outcome assessed at the Week 6 visit is evidence of suture or mesh exposure at the site of the sacrocolpopexy mesh. The POP-Q examination will be performed, as well as a vaginal examination (speculum and digital) to assess for suture or mesh exposure. In addition, pain and analgesic use and adverse events will be reviewed. All efforts will be made by site staff to ensure both follow-up anatomic measurements (POP-Qs) will be conducted by a healthcare provider other than the treating surgeon to reduce bias on outcomes after the study procedure. In the event the treating surgeon is the only qualified healthcare provider at the site trained in the POP-Q, the follow-up anatomic measurements will be conducted by the treating surgeon.

The Week 6 Visit consists of the following:

- Participant Contact Form update
- Assessment of pain and analgesic use
- Review of Adverse Events (if applicable)
- POP-Q Exam
- Vaginal examination (speculum and digital) to assess for suture or mesh exposure

Month 6 Phone Call (± 4 weeks)

Patients will be contacted by phone 6 months postoperatively to review contact information, pain and analgesic use, and adverse events.

The Month 6 Call consists of the following:

- Participant Contact Form update
- Assessment of pain and analgesic use
- Review of Adverse Events (if applicable)

Year 1 Visit (± 4 weeks)

The primary outcome assessed at the Year 1 visit is evidence of suture or mesh exposure at the site of the sacrocolpopexy mesh. The POP-Q examination will be performed, as well as a vaginal examination (speculum and digital) to assess for suture or mesh exposure. In addition, pain and analgesic use and adverse events will be reviewed. Participants will also complete the PFIQ-sf7, PISQ-IR, and PFDI-sf20. All efforts will be made by site staff to ensure both follow-up anatomic measurements (POP-Qs) will be conducted by a healthcare provider other than the treating surgeon to reduce bias on outcomes after the study procedure.

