Data will be entered by study staff at each site into a REDCap database that will be stored on a secure server by the Data Coordinating Center. Study data will be monitored by the Data Coordinating Center as outlined below under Study Monitoring and Documentation. All collected data must be entered into REDCap within 5 business days. Any queries to data entered into REDCap will be addressed by site staff within 5 business days. It is each site's responsibility to regularly check REDCap for data queries. See REDCap Data Entry Protocol for instructions on data entry and query resolution.

Each site will maintain all essential study documents in original format and source documentation that support the data collected on study participants in compliance with ICH/GCP guidelines. Documents must be retained until at least 2 years have elapsed since the formal discontinuation of the clinical investigation. Each site will take measures to ensure that these essential documents are not accidentally damaged or destroyed.

OUTCOME MEASURES

Primary Outcome Measure

The primary outcome of this trial is the incidence of vaginal mesh and suture exposure rates related to the SCP mesh for both arms of the study through 1-year after surgery. Any suture or mesh visible in the vagina that is not at the position of a midurethral sling will be considered a positive outcome. Some participants may also undergo vaginal placement of a mesh sling for stress incontinence in a more distal vaginal location. Exposure of this mesh will not be considered a positive outcome for the primary outcome.

Secondary Outcome Measures

Secondary outcomes that we will measure include a composite of objective and subjective measures, self-reported outcomes, and assessment of complications as outlined below:

1. Assessment of efficacy at 1 year of each type of suture material using the composite cure as outlined below in a-d. Participants will be considered a surgical success for this composite outcome if each of the following four criteria are met:
 - a) Anatomic success: Leading edge of the prolapse is at or above the hymen (POP-Q point Ba and Bp \leq 0) and the vaginal apex descends less than 1/3 of the total vaginal length (C $<$ - TVL/3)
 - b) Subjective success: Patient denies symptoms of vaginal bulging per PFDI-20 question 3, answering "No" or "Yes" but "Not at All" bothersome (< 2)

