 - c) Assessment for re-intervention or re-surgery for recurrence or persistence of POP: No need for pessary use or additional surgical treatment for prolapse at any time after the initial procedure
 - d) No mesh / suture exposure
2. Assessment of participant changes in QoL, symptom bother, and sexual functioning at 1 year compared to baseline^{30,31}:
 - PFDI 20-Pelvic Floor Distress Inventory
 - PFIQ-7-Pelvic Floor Impact Questionnaire
 - PISQ-IR-Pelvic Organ Prolapse/Urinary Continence Sexual Questionnaire

3. Assessment of procedure-related or pelvic floor-related adverse outcomes in each group as classified according to the Clavien-Dindo surgical complication grading scale²⁹. Adverse events will be assessed intra-operatively, at 6 weeks, 6 months, and 1 year postoperatively.

STATISTICAL CONSIDERATIONS

Statistical Methods

Data analyses will include t-tests for continuous data, chi-square or Fisher's exact for categorical data, and multi-variable regression to assess the effects of any bivariate analyses found to have a positive relationship. Confidence intervals will be reported for continuous data and will be included in the assessment and reporting of outcomes. When the data are analyzed, both chi square and Fisher's exact analyses are performed and the appropriate test and associated p value will be used based on the proportion of samples with input less than 5% of the total population. Those with a small output will utilize Fisher's exact.

The data will be analyzed as Intent to Treat. Missing data may occur if subjects fail to return for follow up, thus we plan to over-recruit in order to account for a 20% drop-out rate. Since study participants are undergoing surgery, they are more likely to return for their follow-up visits since these are part of their standard post-operative care. This will decrease the rate of drop-outs. The fact that this is an RCT will minimize the chance of a differential drop-out rate between the groups.

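### The primary-outcome scoring rule is wider than the outcome it serves: read literally, it counts non-randomised cuff and colporrhaphy sutures as events in both arms

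*Combined protocol and SAP*

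**What the plan says.** The event is described in several places, and the descriptions do not agree.

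- **Primary Outcome Measure, opening sentence:** the outcome is the "incidence of vaginal mesh and suture exposure rates related to the SCP mesh for both arms of the study through 1-year after surgery". This is a condition on attribution.
- **Follow-Up Visits, Week 6 and Year 1:** the outcome assessed is "evidence of suture or mesh exposure at the site of the sacrocolpopexy mesh". This is a condition on place.
- **Primary Outcome Measure, scoring sentence:** "Any suture or mesh visible in the vagina that is not at the position of a midurethral sling will be considered a positive outcome". The only exception is the sling position.
- **Primary Outcome Measure, sling mesh:** "Exposure of this mesh will not be considered a positive outcome for the primary outcome". The exemption names the primary outcome alone.
- **Secondary Outcome Measures, composite item (d):** "No mesh / suture exposure", with no limit on source or place. Secondary Aim 1 is equally unqualified.
- **Criteria for Study Termination:** an overall mesh and suture exposure rate above 12%, once half the women have had the 6-week check, ends the study. No source limit is given.

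Other sutures lie in the vagina. For the hysterectomy, "The vaginal cuff will be closed using an absorbable suture in 1 layer (suture type at the discretion of the operating surgeon". Under Optional Additional Procedures, "Anterior colporrhaphy may be performed at the discretion of the surgeon", and for the posterior wall, "The surgeon may use a traditional posterior colporrhaphy or defect directed technique"; no suture material is named for either repair. The Week 6 window is minus 2 to plus 4 weeks, counted from discharge, so the first speculum examination falls at about 4 to 10 weeks.

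**The concern.** The trial randomises the suture that fixes the mesh to the vagina. The cuff closure is present in all women in both arms and is not randomised; colporrhaphy sutures are present in some. A site that follows the scoring sentence must count any of these that are still visible. A site that follows the opening sentence or the visit text may not. The protocol text contains no step for identifying which suture was seen and no rule for resolving doubt.

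Events that have nothing to do with allocation, added to both arms, weaken the comparison. This design is sensitive to them because it relies on a 1% rate in the absorbable arm: a background of only 1% roughly doubles that rate. The same count feeds composite item (d) and the 12% termination criterion, which is applied at the visit when closure sutures have had least time to absorb.

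**Working it through.** **Inputs from the protocol (Sample Size):** exposure 10% vs 1%, 80 per arm, power 0.80, type I error 0.1 described as one-sided, uncorrected chi-square, 200 enrolled to allow for 20% loss.

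**Assumed:** a background rate b of visible non-study sutures, equal in both arms and independent of true exposure. The documents give no value, so b = 0, 1, 2, 5 and 10% are shown.

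**Step 1: reproduce the plan's figure.** With mean rate (0.10 + 0.01)/2 = 0.055, the pooled-variance formula is n = 2 × 0.055 × 0.945 × (z_α + z_β)² / 0.09². With z_α = 1.645 and z_β = 0.842 this is 0.10395 × 6.18 / 0.0081 = 79.3, so 80 per arm. Using separate variances under the alternative gives 79. Then 80/0.8 = 100 per arm, or 200. These values correspond to two-sided 0.10, which is one-sided 0.05. A one-sided 0.10 test needs only 57 by the separate-variance formula. Both levels are therefore carried forward.

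**Step 2: add the background.** The observed rate is p′ = 1 − (1 − p)(1 − b). For b = 5%: 1 − 0.90 × 0.95 = 14.5% and 1 − 0.99 × 0.95 = 5.95%. The difference is 8.55 points and the ratio 2.4.

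**Step 3: power.** Exact enumeration of two binomials, n = 80 each, uncorrected pooled z test.

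| b | Rates | Difference (points) | Risk ratio | Power, one-sided 0.05 | Power, one-sided 0.10 |
|---|---|---|---|---|---|
| 0 | 10.0% vs 1.0% | 9.0 | 10 | 89% | 94% |
| 1% | 10.9% vs 2.0% | 8.9 | 5.5 | 80% | 89% |
| 2% | 11.8% vs 3.0% | 8.8 | 4.0 | 73% | 84% |
| 5% | 14.5% vs 6.0% | 8.6 | 2.4 | 57% | 72% |
| 10% | 19.0% vs 10.9% | 8.1 | 1.7 | 42% | 58% |

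The normal approximation starts lower but shows the same pattern: at one-sided 0.05, 81% falls to 75%, 69%, 56% and 42%.

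**Step 4: termination criterion.** Half of 200 is 100 women, so the rate exceeds 12% with 13 or more events. Assume a true 6-week exposure rate of 3% overall (not in the documents). The observed rate is then 1 − 0.97(1 − b), and the binomial chance of more than 12 events is 0.02%, 0.1%, 5% and 51% for b = 1, 2, 5 and 10%. As an upper bound, suppose the planned 1-year rates already applied at 6 weeks: the chance is 0.3% with no background and 1%, 3%, 22% and 75% for the same values of b.

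**The case against.** **The outcome is already tied to the sacrocolpopexy.** A reader of the scoring sentence alone might infer that the event has no link to the study procedure. The documents do not support that: the preceding sentence requires a relation to the mesh, and both visit descriptions give its site. This stands, and it makes the defect a conflict of wording. It does not remove the defect. The sentence that says what is scored is the broad one. The site wording restricts place and not source, and the documents do not say whether a cuff stitch counts as being at the mesh site.

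**The size is assumed.** This also stands. At a 1% background, power is still at or above the planned 80%. The absolute difference, which the plan calls clinically significant, hardly moves.

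**A bias by arm.** One might infer that the present rule favours one suture, because a PDS cuff stitch looks like a PDS graft stitch. It does not follow. Under the literal rule both count, in either arm, so telling them apart is irrelevant. The problem arises only once source must be judged, and the fix has to allow for it.

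**Stopping the trial.** One might infer that cuff sutures would probably end the study early. At 3% true exposure that needs a background near 10%; at 2% the chance is about 0.1%.

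**Sling exposure as composite failure.** This is inferred from the missing exemption in item (d); the text does not state it. Item (d) may simply be shorthand for the primary event.

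**Simplicity.** Counting any visible suture requires no judgement from an examiner, who may be the treating surgeon: a different examiner is sought only for the POP-Q, and with an exception. This advantage is real. In addition, the case report forms are listed but not reproduced, so they may already capture source.

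**Conclusion.** The point holds as a conflict within the outcome definition, in which the sentence used for scoring is the widest of the three and can give a wrong count of primary events. Composite item (d) and the termination criterion carry no source limit either, and whether sling exposure fails the composite is left open.

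The loss is in power and in the risk ratio, with little change in the risk difference. It ranges from minor at a 1% background (89% to 80% at one-sided 0.05; 94% to 89% at one-sided 0.10) to serious at 5% or more (57% or lower; 72% or lower). Where the trial falls in that range depends on a background rate that the documents do not give, taken here as equal in the arms and independent of true exposure. It should be corrected because the remedy is cheap and the source of a suture cannot be reliably reconstructed if it was not noted when seen.

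**What to change.** 1. Reword the scoring sentence: an event is sacrocolpopexy mesh, or a suture placed to attach that mesh to the vagina, visible in the vagina. State that material from cuff closure, colporrhaphy or a sling is not an event.
2. Use the same definition in the Week 6 and Year 1 visit text, in composite item (d), and when calculating the exposure rate for Criteria for Study Termination. The threshold itself is not at issue here.
3. Record the material, location and judged source of each visible suture or mesh on the examination form, with a 'cannot tell' option. Record the cuff-closure material on the Surgical Procedures Form.
4. Report the primary comparison also with any visible suture or mesh as the event, and with 'cannot tell' findings counted once as events and once as non-events. Such findings may be more common in the PDS arm, where cuff and graft sutures can be the same material, so fixing a single rule for them could itself bias the comparison.

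Cost: a few sentences and form items, with no added visit or examination. The downside is that attribution brings in examiner judgement, possibly the treating surgeon's; the any-visible analysis is kept alongside for that reason.

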1. To compare the 1-year composite success rate (*leading edge of prolapse is at or above the hymen and apex has descended less than 1/3 of the vaginal length, no subjective feeling of bulge; no retreatment for pelvic organ prolapse (POP); no vaginal mesh/suture exposure*) of permanent versus delayed absorbable sutures for mesh graft attachment during robotic total hysterectomy and sacrocolpopexy.
2. To compare postoperative symptoms of pelvic floor disorders, including urinary incontinence, voiding dysfunction, pelvic organ prolapse, sexual dysfunction and quality of life between the 2 groups at 1 year.
3. To evaluate adverse outcomes in each group, classified according to the Clavien-Dindo system.

BACKGROUND

Symptomatic pelvic organ prolapse is common and 13%¹ to 19%^{2,3} of women undergo surgical repair. Reconstructive pelvic surgery is broadly divided into procedures that rely on existing native tissue versus the use of graft augmentation, either with synthetic or biologic materials. Native tissue vaginal repair, while associated with the lowest rate of surgical complications,⁴ has a high rate of recurrent prolapse. A recent randomized trial of uterosacral versus sacrospinous ligament fixation for POP demonstrated a 30% recurrence rate at 2 years.³

Abdominal sacrocolpopexy (SCP) is considered to be the most durable operation for advanced pelvic organ prolapse with reoperation rates of less than 5%.⁵⁻⁷ Minimally-invasive techniques of SCP, such as robotic-assistance, are associated with improved recovery times and less cost than abdominal SCP without a demonstrable difference in efficacy.^{8,9} While traditionally reserved for women with vaginal vault prolapse, SCP is increasingly considered as a primary surgical option for women who present with uterovaginal prolapse in an attempt to improve longer-term surgical outcomes. The optimal management of the uterus and cervix in these cases is unclear.

Rationale for total versus supracervical hysterectomy with concomitant SCP

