The effect of suture on mesh exposure may be as significant as concomitant hysterectomy or mesh type. At UNC, we reported on mesh exposure using a permanent suture for mesh attachment during SCP with and without concomitant total hysterectomy, with rates of 8% at 1 year.²⁴ There is some evidence that a delayed absorbable suture may reduce the risk of mesh or suture erosion. In a retrospective review comparing braided permanent suture to delayed absorbable monofilament suture for SCP mesh attachment, rates of mesh exposure were reduced in the absorbable suture group (3.7% vs 0%), with no associated POP recurrence.²⁵ Similarly, in another retrospective review, when delayed absorbable monofilament suture was used for SCP mesh attachment in 67 women undergoing total abdominal hysterectomy and SCP, no mesh exposures were noted at a median follow up of 27 months.²⁶ The use of permanent sutures for vaginal mesh attachment has historically been advocated as a means to reduce POP recurrence risk; yet, no prospective study has definitively answered this question. The tradeoff of using a permanent suture may be an increased risk of mesh or suture exposure, as a permanent suture that has breached the vaginal epithelium may serve as a nidus for bacterial seeding, theoretically increasing the risk of mesh exposure. **As SCP appears to be a more durable procedure for women with advanced uterovaginal prolapse, there is an urgent need to identify the ideal method of vaginal mesh attachment that minimizes the risk of mesh-related complications while maintaining effectiveness of the POP repair.**

Choice of mesh material

Upsylon™ (Boston Scientific, Natick, MA) is a pre-formed Y-mesh that is light-weight (25 g/m²), composed of Type I polypropylene material, with a pore size of 2.8 mm² and surface area ration of 1.11. It was FDA approved in 2012. The mesh is blue in color that may aide in the ability to detect even small areas of mesh exposure and erosion. No data currently exist regarding the performance of this particular mesh product in SCP. It is lighter in mesh weight than the IntePro™ y-mesh (American Medical Systems, Minneapolis, MN), which we previously used in the comparative trial of robotic to abdominal SCP in which our mesh exposure rates were 8%.

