The rate of reported mesh exposure varies greatly from 0-27%, as discussed in our Background section on page 2 of the Investigator Protocol. Based on published data both at our institution and elsewhere in the literature, we determined that a 10% and 1% rate of mesh exposure in the two groups is both supported by data and clinically relevant, thus we are estimating a 9% difference in mesh erosion rates between the two groups: 1% vs 10%. This is a clinically significant difference that would affect a change in clinical practice.

Sample Size

The power calculation was performed using the statistical computation software Epi Info™ 7.1.3.10, developed on 3/11/14. It is a trademark of the Centers for Disease Control and Prevention and uses chi square for its computation of sample size for studies based on categorical data comparison such as the current study.

We are planning a study of independent cases and controls with 1 control(s) per case. Prior data indicate that the mesh exposure rate among controls is 10%. If the mesh exposure rate for experimental subjects is 1%, we will need to study 80 experimental subjects and 80 control subjects to be able to reject the null hypothesis that the failure rates for experimental and control subjects are equal with probability (power) 0.8. The Type I error probability associated with the test of this null hypothesis is 0.1. The alpha of 0.1 is based on a one-sided hypothesis, estimating that mesh exposure rates will be higher in the study arm using permanent suture compared to the study arm using absorbable suture. We will use an uncorrected chi-squared statistic to evaluate this null hypothesis. We plan to enroll a total 200 subjects across sites to account for up to 20% loss to follow up, thus the use of chi square is appropriate given the adequately large sample size.

We feel the sample size is appropriate based on our sample size calculation, taking into account the estimated rates of mesh exposure in the two groups, as well as our clinical judgment of the number of procedures that are performed each year at the study sites. In the past year each

study site has performed 50 cases, for a total of 200 cases at all combined sites. Therefore our sample size of 100 subjects per study arm is feasible for completion in the time allotted.

Primary Hypothesis

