Statistical testing will be performed to determine if the incidence of mesh and suture exposure in the absorbable suture arm is non-inferior to the permanent suture arm. The null hypothesis is that the incidence of mesh and suture exposure in the absorbable suture arm will be equal to the incidence of mesh and suture exposure in the permanent suture arm.

Secondary Hypotheses

1. Statistical testing will be performed to determine if the composite success rate in the absorbable suture arm will be non-inferior to the permanent suture arm. The null hypothesis is that the success rate in the absorbable suture arm is less than or equal to the success rate in the permanent suture arm.
2. Statistical testing will be performed to determine if the symptomatic success rate in the absorbable suture arm is non-inferior to the permanent suture arm. The null hypothesis is that the success rate in the absorbable suture arm is less than or equal to the success rate in the permanent suture arm.
3. Statistical testing will be performed to determine if the AE incidences rate of the absorbable suture arm is non-inferior to the permanent suture arm. The null hypothesis is that the AE incidences rate in the absorbable suture arm is greater than or equal to the rate in the permanent suture arm.

STUDY MONITORING AND DOCUMENTATION

The Principle Investigator will monitor the study and assess the need for amendments as the study progresses. If a protocol revision is necessary for reasons including but not limited to the rights, safety or welfare of participants, or scientific integrity of the data, an amendment is required. Appropriate approvals (e.g., IRB) of the revised protocol must be obtained prior to implementation at each site.

Site Documentation

All study documents included in this protocol that will be presented to subjects will be submitted to the IRB for approval. Each site will maintain a site study binder that will include the following:

- Enrollment log of patients who have consented to be in the study (electronic version)
- Protocol Deviation Log (electronic version)
- Adverse Event Log (electronic version)
- Investigator protocol and amendments
- IRB submissions, modifications, renewals
- Data Coordinating Center monitoring correspondence
- DSMB reports
- IRB approved Informed Consent Form

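### The secondary success composite counts mesh/suture exposure as failure, so an exposure benefit for absorbable suture can offset extra prolapse failure that no other planned test fully covers

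*Combined protocol and SAP*

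**What the plan says.** Outcome Measures, Secondary Outcome Measures, item 1 introduces the composite as "Assessment of efficacy at 1 year of each type of suture material using the composite cure as outlined below in a-d". The rule is strict: "Participants will be considered a surgical success for this composite outcome if each of the following four criteria are met". The criteria are (a) anatomic success on POP-Q, (b) no bothersome bulge, (c) no pessary or repeat surgery for prolapse, and "d) No mesh / suture exposure". Secondary Aim 1 defines success the same way and includes "no vaginal mesh/suture exposure".

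Under Secondary Hypotheses, item 1, the composite is tested to "determine if the composite success rate in the absorbable suture arm will be non-inferior to the permanent suture arm". No margin is given, and the stated null is that absorbable success is at or below permanent success.

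Exposure is also the primary outcome. Statistical Methods gives the planned rates: "thus we are estimating a 9% difference in mesh erosion rates between the two groups: 1% vs 10" (percent). Sample Size gives the direction: "estimating that mesh exposure rates will be higher in the study arm using permanent suture compared to the study arm using absorbable suture".

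The Background section on suture material supplies the other side of the trade-off: "The use of permanent sutures for vaginal mesh attachment has historically been advocated as a means to reduce POP recurrence risk". It adds that this has not been settled prospectively, and it calls for a method that limits mesh complications while keeping the repair effective.

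**The concern.** The Background sets two properties against each other: exposure, where absorbable suture may be better, and durability of the repair, where it might be worse. To judge that trade-off, each property has to be measured without the other. The composite named as the efficacy assessment combines them. A woman with a perfect repair and a visible suture is a failure, and the plan expects about ten such women with permanent suture for every one with absorbable suture.

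Absorbable suture could therefore match permanent suture on success while more repairs fail, and the result could be read as showing that durability was maintained. The exposure benefit would also be counted twice, once as the primary outcome and again within the efficacy measure.

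**Working it through.** **Inputs.** Exposure rates of 10% (permanent) and 1% (absorbable) come from Statistical Methods and Sample Size. The Background gives two other figures: 8% at 1 year with permanent suture, and 3.7% vs 0% in a retrospective comparison of braided permanent with absorbable suture. The documents give no 1-year failure rate on a–c. The nearest figures are reoperation below 5% after sacrocolpopexy and 30% recurrence at 2 years after native-tissue repair. I assume 5–20% and show 30% as an extreme. The overlap between exposure and prolapse failure is also not given, so it is varied below.

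**The plan's own figure.** The 10% vs 1% rates do drive the design. For an uncorrected chi-square test with power 0.80,

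n = [z_α·√(2·0.055·0.945) + 0.8416·√(0.09 + 0.0099)]² / 0.09².

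With z_α = 1.645 this gives 79 per arm, against the stated 80, and 160/0.8 = 200 as stated. (That z_α is two-sided 0.10, or one-sided 0.05. One-sided 0.10 as worded gives 57. This is a separate matter.)

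**Break-even under independence.** Let e be exposure and f be failure on any of a–c. Composite success is (1 − e)(1 − f). The arms are equal when 0.90(1 − f_P) = 0.99(1 − f_A), so the concealed excess is f_A − f_P = (1 − f_P) × 0.09/0.99.

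| Permanent a–c failure | Absorbable a–c failure at equal composite | Composite, both arms | Concealed excess (points) |
|---|---|---|---|
| 5% | 13.6% | 85.5% | 8.6 |
| 10% | 18.2% | 81.0% | 8.2 |
| 15% | 22.7% | 76.5% | 7.7 |
| 20% | 27.3% | 72.0% | 7.3 |
| 30% | 36.4% | 63.0% | 6.4 |

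Conversely, if a–c failure is the same in both arms at 5–20%, the composite favours absorbable suture by 0.09(1 − f), which is 8.6 to 7.2 points, through exposure alone.

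**Other exposure rates.** These use the same formula with a–c failure of 5–20%.
- 8% vs 1%: (1 − f_P) × 0.07/0.99 = 6.7 to 5.7 points.
- 3.7% vs 0%: (1 − f_P) × 0.037 = 3.5 to 3.0 points.
- No difference in exposure: zero.

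**Overlap.** Suppose a share q of exposed women in each arm also fail on a–c. Composite failure is then e + f − eq, and the concealed excess at the planned rates is 9(1 − q) points. This is 9.0 at q = 0, 7.2 at q = 0.2, 4.5 at q = 0.5 and zero at q = 1.

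**Effect on a non-inferiority conclusion (illustration only).** The plan has no margin, so I assume one. Take true a–c failure of 10% vs 18.2%, 80 per arm, one-sided 0.05 and a normal approximation.
- Four-item composite: SE = √(2 × 0.81 × 0.19/80) = 0.0620. With a 10-point margin the chance of passing is Φ(0.10/0.0620 − 1.645), about 49%.
- a–c only: SE = √((0.09 + 0.1488)/80) = 0.0546. The chance is Φ((0.10 − 0.0818)/0.0546 − 1.645), about 10%.
- With a 15-point margin the two figures are about 78% and 35%.

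**What else is tested.** Secondary hypothesis 2 tests symptomatic success. Hypothesis 3 compares adverse event incidence, and prolapse is listed among the events related to the pelvic floor. No hypothesis covers anatomic failure, retreatment, or a–c together, and nothing commits to reporting the components by arm.

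**The case against.** Several points on the other side have force.

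- **Recurrence is not said to be expected.** A reader might infer that the protocol predicts more recurrence with absorbable suture. It does not. It reports a historical argument for permanent suture, calls the question unsettled, and cites retrospective data with no associated recurrence. This stands: it is an open question, not a predicted harm.
- **Recurrence is partly covered elsewhere.** Symptomatic success is tested separately, Secondary Aim 2 compares prolapse symptoms, and prolapse can be a reportable adverse event. This stands for symptoms. The adverse event comparison is only partial cover, because it pools all reportable events and may itself include exposures.
- **Break-even is not declared success.** A reader might infer that the trial would declare absorbable suture non-inferior despite 7–9 points of extra failure. Under the null as written, equal composites lie inside the null and would be rejected only at about the alpha rate. A higher chance depends on how the undefined margin is filled in, which is why the margin calculation is only an illustration.
- **A net-success composite is legitimate.** Counting exposure as surgical failure is defensible, it is openly and consistently defined, and exposure is reported separately as the primary outcome. This stands as a reason to keep the four-item version. It does not make that version a measure of durability.

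**Conclusion.** The concern holds in a limited form. Because exposure is a required part of the efficacy composite, an exposure benefit for absorbable suture can offset extra prolapse failure. The concealed amount is about 7–9 points if the full planned benefit occurs, the events are independent, and permanent-arm a–c failure is 5–20%. The last two conditions are assumptions. The amount shrinks with a smaller exposure benefit or more overlap, and vanishes without a benefit. It is greatest when the primary hypothesis succeeds most clearly, which is the result the plan says would change practice.

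The uncovered gap is anatomic failure, retreatment and the a–c combination; symptomatic recurrence has its own test. The documents do not support reading this as a flaw in the primary outcome, its test or the sample size, none of which depends on the composite. It should be fixed as a cheap improvement to a secondary outcome.

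**What to change.** - Prespecify the a–c composite (anatomy, bulge symptom, no retreatment) as the durability comparison for secondary hypothesis 1.
- State a non-inferiority margin with its justification, and replace the null with one that matches it: absorbable success is lower than permanent success by at least the margin. Removing (d) while keeping the present null would leave a test of superior durability, which cannot show that durability is maintained.
- Keep the four-item a–d composite as a net-benefit outcome, labelled as such.
- Report each of a–d by arm.
- Align Secondary Aim 1, Secondary Outcome Measures item 1 and Secondary Hypotheses item 1.

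The cost is wording and one table. The existing composite already requires every component, so no new visits or participants are needed. There are two downsides. The success comparison may look less favourable to absorbable suture. Precision is also limited, because the trial was sized for exposure: with 10% a–c failure in both arms and 80 per arm, SE = √(2 × 0.09/80) = 4.7 points, so a one-sided 95% bound lies 1.645 × 4.74 = 7.8 points from the estimate. The plan should say so when it sets the margin.
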